5.3 Supportive Care

Hematopoietic growth factors will be administered as per standard of care. All chemotherapy and growth factors will be used from commercial sources.

5.4 Dose Modifications

Every attempt will be made to deliver a minimum of 1 cycle of AI chemotherapy to each patient on the AI regimen. In the case of the specific adverse events related to chemotherapy, dose reductions of doxorubicin and/or ifosfamide may be carried out as per standard practice.

5.5 Duration of Therapy:

Cycle 1 will be considered as the study cycle.

Patients can receive up to a total of 6 cycles of chemotherapy in the absence of progressive disease and intolerable toxicity related to the study drug. Patients can receive Rolapitant or fosaprepitant, whichever arm they were assigned originally, in subsequent cycles (cycles 2-6). The patients will continue to report adverse events including nausea/vomiting in daily symptom record diary during cycles 2-6. In addition, the patients need to fill out the FLIE questionnaire (Appendix E) in cycle 1 (e.g. days 5 and 10) to monitor the improvement in nausea/vomiting.

Therapy will be continued for at least 1 cycle unless there is a rapid progression of disease, and for additional 5 cycles, if there is stable or responding disease and if unacceptable toxicity is not observed (maximum total 6 cycles).

6.0 Pretreatment Evaluation

- Standard History and Physical examination including weight and height.
- Karnofsky performance status > 60% (PS appendix D)
- Laboratory studies will include a CBC with differential, and platelet count, electrolytes and serum chemistries.
- Serum beta hCG or urinary pregnancy test (when indicated).
- All screening labs/pretreatment evaluations can be done within 30 days before registration.

7.0 Evaluation During Study

- Interim History and Physical examination including weight will be done before each cycle of chemotherapy.
- Patients will report on daily symptom record diary the adverse events, the date of all emesis episodes, intensity of nausea, and rescue medications before and during study on days 1-10 of the first cycle. Also, patients will report the functional evaluations of nausea and emesis according to Functional Living Index-Emesis (FLIE) scale in cycle 1 (e.g. days 1, 5 and 10) (26). In addition, the patients will continue to report on daily symptom record diary the adverse events while on study.
- Serum electrolytes and chemistries will be performed prior to every cycle and as frequently as needed during the cycle to monitor the toxicity
- Management of hypersensitivity to the study drug: Patients with allergic reactions can be symptomatically managed. All patients with grade 4 hypersensitivity reactions (anaphylaxis) will be removed from the study.

8.0 End of Study/Early Withdrawal

At their last clinic visit on the study, standard History and Physical examination including weight will be documented. Laboratory studies will include a CBC with differential, and platelet count.

9.0 Criteria for Response

9.1 Response

All patients who receive one dose of study drugs (Rolapitant and fosaprepitant) under this protocol will be evaluable for response and toxicity.

9.2 The severity of nausea will be reported in patients diary using 4-point scale (Likert scale), as 0 (none), 1 (mild), 2 (moderate), and 3 (severe) during cycle-1 of chemotherapy.

9.3 Response will be defined as 0-24 hours, 24-120 hours, 120-240 hours, and overall period.

Complete response (CR): No emetic episodes and no rescue medications. **Complete control (CC):** CR and no more than mild nausea.

9.4 Toxicity: Toxicities will be graded using the Common Terminology Criteria for Adverse Events v4.03 – CTCAE (see Appendix C). Uncomplicated, severe, or life threatening neutropenia and thrombocytopenia are expected toxicities of the study chemotherapy regimen and as such will not be collected as adverse events in this study since the data is already captured through the PDMS/CORE.

10.0 Criteria for Discontinuation from Treatment

Patients may be discontinued from study treatment at any time. Specific reasons for discontinuing treatment include the following:

- Serious or life-threatening adverse event
- Risk to patients as judged by the Investigator and/or Sponsor
- Severe noncompliance with protocol as judged by the Investigator and/or Sponsor
- Request of the patient
- Patient becomes pregnant
- Progressive disease
- Investigator becomes aware of conditions or events that suggest a possible hazard to patients if the clinical study continues

10.1 Discontinuation from Study

Patients who discontinue from treatment will continue to receive follow-up assessments as part of the study unless they are discontinued from study by one of the following events:

- Withdrawal of consent
- Loss to follow-up
- Death from any cause
- Termination of the study

11.0 Statistical Consideration and Sample Size

Statistical Considerations and Analysis

This is a phase II trial to study the treatment efficacy of rolapitant on nausea/vomiting in patients with sarcoma receiving multi-day chemotherapy with doxorubicin and ifosfamide regimen (AI). This trial will be carried out in two parts. The primary goal of the first part of the trial is to estimate the preliminary efficacy of rolapitant administered as single-dose on Day 1 by evaluating complete response (CR) rate in a single-arm setting. The primary objective of the second part of the trial is to establish the efficacy of rolapitant

administered as single-dose on Day 1 by evaluating CR rate in comparison with the efficacy of fosaprepitant administered as single-dose on Day 1.

Design and sample size/power

Part I: A single-arm phase II study of rolapitant administered as single-dose on Day 1

We will assess the efficacy of rolapitant on nausea/vomiting by evaluating CR rate using the Simon's Minimax 2-stage design (27). A patient will be considered as to have a CR if s/he does not experience chemotherapy related emesis and do not need rescue medication during cycle-1 following initiation chemotherapy. The primary endpoint is CR rate in cycle 1 (days 1-10). In our previous study, we observed 2 (11%) CRs among 18 patients who were treated with the standard of care. Based on the data of the 19 patients currently enrolled into this study, 6 out of 19 patients (32%) experienced CR. Therefore, a CR rate of 11% or less is considered as clinically insignificant, while a CR rate of 32% or higher is considered as clinically significant. When the probability of accepting an ineffective regimen (CR rate ≤ 11%) is 0.05 and the probability of rejecting an effective regimen (CR rate \geq 32%) is 0.05, the Simon Minimax 2-stage design requires 24 patients in the first stage. The drug will be rejected if no more than 2 responses are seen in the first stage. Otherwise, another 18 patients will be accrued. At the end of the trial, the drug will be rejected if no more than 8 responses are observed in a total of 42 evaluable patients (maximum accrual 47 patients; 42 evaluable, potential 10% drop out rate). The trial will be stopped early 50% of the time, and the mean sample size of the trial will be 33 if the true response rate is 11%. Accrual will be halted after the 24th patient is enrolled until 3 or more responses are seen in the first stage.

Since there is no interaction between rolapitant and CYP3A4, the dose of dexamethasone will not be reduced from 12 mg to 8 mg and will be kept constant at 12 mg on Days 2-5 for Part 1 (Rolapitant), and Arm A (Rolapitant) of the Part 2 as stated in "Treatment Plan" section. After 9 patients were accrued to the first phase of Part I of the study with a dose of dexamethasone at 8 mg on Days 2-5, the protocol was amended to keep dexamethasone dose constant at 12 mg on Days 2-5. Up to date, 19 patients have been enrolled and treated with dexamethasone at 12 mg on Days 2-5 as a new cohort for the first stage of the Simon's Minimax 2-stage design, additional 5 patients will be accrued and treated in the first phase of Part I of the study as soon as this amendment is approved by IRB. The same rules of the design aforementioned will be applied.

Part II: A randomized, 2-arm phase II study of rolapitant vs fosaprepitant

The decision to move on to Part II of this study will not depend on the results of the patients who have been treated with dexamethasone at 8 mg on Days 2-5. Rather, if the first part of the trial for the patients who will be treated with dexamethasone at 12 mg on Days 2-5 was not stopped early due to lack of efficacy of rolapitant, the trial will proceed to the second part of the trial. This will be a randomized, 2-arm trial of rolapitant administered as single-dose on Day 1 in patients with sarcoma receiving multi-day

chemotherapy with Doxorubicin and Ifosfamide regimen (AI). Arm A patients will receive a single dose of rolapitant on Day 1; Arm B patients will receive a single dose of fosaprepitant on Day 1. The primary objective is to evaluate the effect of rolapitant on nausea/vomiting as compared to the effect of a single dose of fosaprepitant in cycle 1 (days 1-10). Again, a patient will be considered as to have a complete response (CR) if s/he does not experience emesis and do not need rescue medication during cycle-1 following initiation chemotherapy. The primary endpoint is CR rate in cycle 1 (days 1-10). The sample size for this part of the trial will depend on the CR rate observed in the first part of the trial. Table 1 shows sample sizes required for three presumably observed CR rates in the first part of the trial assuming that the CR rate in Arm B is 11%. For example, a total of 78 patients, 39 in each arm, will provide the study 80% power to detect the differences of CR rates between the two arms using a Fisher exact test with a 0.05 twosided significance level when the respective CR rates are 40% and 11% in Arm A, and B (15, 16). All patients that complete cycle-1 (days 1-10) of chemotherapy will be considered evaluable for the study. Patients that can't complete cycle-1 of chemotherapy due to disease progression, treatment change, withdrawal of consent, or other reasons will be replaced with new patients (maximum accrual 86 patients; 78 evaluable, potential 10% drop out rate) nQuery 7.0 was used for the sample size or power calculation.

Table 1. Sample size needed per arm in testing difference in complete response rate during cycle-1 between Arm A and B, Fisher's exact test with two-sided significance level of 0.05 and 80% power assuming the CR rate of Arm B is 11%

CR rate in Arm A	30%	40%	45%	50%
Sample size	78	39	31	24

Analysis Plans

Patients' demographic and clinical characteristics at baseline will be summarized using descriptive statistics such as mean, standard deviation, median, interquartile range (IQR), frequency where appropriate. We will apply Student t-test/Wilcoxon test and Kruskal-Wallis test/ANOVA to compare continuous variables between different patient group, and the chi-square test or the Fisher's exact test to assess the association between two categorical variables (28).

For the analysis of the primary endpoint of the first part of the trial, we will provide point estimate along with 95% exact confidence interval (CI) of CR rate.

For the analysis of the primary endpoint of the second part of the trial, Fisher exact test will be used to test the difference of CR rates between the two arms. CR rates along with their 95% confidence intervals (CIs) will be estimated by study arm. We will use logistic regression model (28) to assess the effect of patient specific covariates, such as treatment group, gender, etc. on the complete response. The secondary endpoints are the response rates in each of the time periods (0-24 hours, 24 hrs-120 hrs, and 120-240 hours). Logistic regression models using generalized estimating equations (GEE) will be

used to fit the response data to take the intra-patient correlation into account and to compare the differences of the response rates between the two treatment arms and to evaluate the effects of the patient specific covariates(29).

Toxicity data will be summarized by frequency tables for all patients and by treatment arm. For the efficacy endpoint, intent-to-treat analysis will be applied to the eligible patients. For the toxicity endpoint, per-treated analysis will be used to include any patient who received the treatment regardless of the eligibility nor the duration or dose of the treatment received.

If there are missing data, the reasons for missing data will be recorded, and missing-data mechanism will be checked. For data missing at random (MAR), multiple imputation techniques implemented in SAS PROC MI procedure to handle missing data will be used. For data missing not at random (MNAR), methods that add an explicit model for the missing mechanism to the data model will be applied.

The data from the patients who were treated with dexamethasone at 8 mg on Days 2-5 (prior to amendment 2) will be analyzed separately and included in relevant reports.

Randomization

Randomization will be carried out via CORe.

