2.4.6 Study Update

To date, 28 patients have been enrolled on to this study, all of them have completed more than 1 cycle of treatment. The treatment of Rolapitant is well tolerated. In the first cohort- Cohort 1 (dexamethasone 12 mg on day 1, and 8 mg on days 2-5), none of the 9 patients had complete response in days 1-10. Since there is no interaction between Rolapitant and CYP3A4, the amendment 2 was written to keep the dose of dexamethasone constant at 12 mg on Days 2-5 for Part 1 (Rolapitant). In this new cohort- Cohort 2 (dexamethasone 12 mg on days 1-5), the complete response rate (no emetic episodes and no rescue medications) was 29% (5/19) in days 1-10; and the complete response rate was 32% (6/19) for emetic episodes only related to chemotherapy. We therefore would like to expand our experience with the current regimen to confirm the response rate prior to initiation of Part 2 of the study.

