13.2 Adverse Events

An adverse event (AE) is any new, undesirable medical occurrence or change (worsening) of an existing condition in a subject that occurs during or after treatment, whether or not considered to be product related. Therefore, adverse events are treatment-emergent signs or symptoms. In this study, the following adverse effects are expected and will not be reported. They will be summarized in the updated and final analysis. Myelosuppression and its associated complications are part of the treatment of sarcoma with high dose AI. Therefore, low blood counts and related complications such as infections, bleeding and hospitalizations due to myelosuppression will not be reported as severe adverse drug reactions related to Rolapitant.

AEs will be collected from the time of informed consent to 30 days after last study drug administration. AEs that occur before the first study drug administration, concomitant illnesses, which existed before study entry, but did not worsen during the treatment period and any pre-existing conditions are known as "pre-treatment AEs" and by definition are "unrelated" to study drug. All AEs, regardless of the source of identification (e.g., physical examination, laboratory assessment, electrocardiograms [ECG], reported by patient), must be documented.

Each AE will be assessed by the Investigator with regard to the intensity. Intensity should be assessed in accordance with the Common Terminology Criteria for Adverse Events (CTCAE v.4.03, Appendix C). Attribution of adverse events (AE) to study treatment will be recorded as follows:

- Related: The AE is clearly related to the study treatment.
- Possible Related: The AE may be related to the study treatment.
- Unlikely Related: The AE is doubtfully related to the study treatment.
- Unrelated: The AE is clearly NOT related to the study treatment.

Follow-up of Adverse Events

All AEs experienced by a patient, irrespective of the suspected causality, will be monitored until the AE has resolved, any abnormal laboratory values have returned to baseline or stabilized at a level acceptable to the Investigator, until there is a satisfactory explanation for the changes observed, until the patient is lost to follow-up, or until the patient has died.

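### Complete response, the primary endpoint of both parts, counts only chemotherapy-related emesis in Part I but any emesis in Section 9.3 and Part II

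*Combined protocol and SAP*

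**What the plan says.** Section 11.0, Part I, defines the primary endpoint over days 1-10 of cycle 1: "A patient will be considered as to have a CR if s/he does not experience chemotherapy related emesis", with no need for rescue medication. The same paragraph takes its 32% target from 6 of 19 current patients and its 11% floor from 2 of 18 patients in a previous study. It rejects the drug at 2 or fewer responses in 24, or 8 or fewer in 42.

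Section 9.3 defines CR without the qualifier: "No emetic episodes and no rescue medications".

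Section 11.0, Part II, also omits it: "Again, a patient will be considered as to have a complete response (CR) if s/he does not experience emesis". The sizing rule for Part II reads: "The sample size for this part of the trial will depend on the CR rate observed in the first part of the trial".

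Section 2.4.6 reports both measures in the 12 mg dexamethasone cohort: the rate without the qualifier "was 29% (5/19) in days 1-10; and the complete response rate was 32% (6/19) for emetic episodes only related to chemotherapy".

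On data collection, Section 7.0 has the diary record "the date of all emesis episodes, intensity of nausea, and rescue medications". The only attribution scale in the protocol is in Section 13.2: "Attribution of adverse events (AE) to study treatment will be recorded as follows".

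**The concern.** A fixed cutoff works only if everyone counts the same thing. Here a reader who follows Section 9.3 and a reader who follows Section 11.0, Part I, can classify the same patient differently, and one patient has already been classified differently. The final Part I decision could therefore depend on which section is applied. A rate measured on one definition is also set to determine the size of a randomized comparison that tests the other.

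The narrower definition needs a judgement that the plan does not describe. Setting aside emesis judged unrelated to chemotherapy can only raise the CR count, and in a single-arm part that judgement is made knowing the treatment. If the definition is settled only after the final count, the choice will be made with the result in view.

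**Working it through.** **Inputs.** From Section 11.0: floor 11% (2/18), target 32% (6/19), boundaries 2/24 and 8/42, and for Part II a two-sided 0.05 Fisher exact test with 80% power against 11%. From Section 2.4.6: 5/19 and 6/19. Section 5.1 words the Part I boundaries differently; that is a separate matter, and the Section 11.0 boundaries are used here.

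**1. Part I as stated.** P(accept | p) = sum over x = 3 to 24 of P[Bin(24, p) = x] × P[Bin(18, p) ≥ 9 − x].
- p = 0.11: 0.036. Early stop P[Bin(24, 0.11) ≤ 2] = 0.499. Mean size 24 + 18 × (1 − 0.499) = 33.0.
- p = 0.32: 0.951.

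The plan's figures (error rates of 0.05, early stop 50%, mean size 33) reproduce.

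**2. The two counts.** 6/19 = 31.6%. 5/19 = 26.3%, although Section 2.4.6 prints 29% (5/17 would be 29.4%). Both 26.3% and 29% are carried below as a range for the any-emesis rate.

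**3. Stage 1.** Five and six both exceed 2, so stage 1 is cleared under either definition.

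**4. Final Part I decision from here.** 42 − 19 = 23 patients remain, and acceptance needs 9 responses. Any emesis needs 9 − 5 = 4 more; chemotherapy-related only needs 9 − 6 = 3 more. Every any-emesis CR is also a CR on the narrower definition, so the chance of opposite decisions is the difference between the two pass probabilities.

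| Assumed rates (any emesis; chemotherapy-related) | P(4 or more of 23) | P(3 or more of 23) | Opposite decisions |
|---|---|---|---|
| 5/19; 6/19 | 0.891 | 0.989 | 0.098 |
| 0.29; 0.32 | 0.934 | 0.990 | 0.056 |

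Whenever they disagree, the chemotherapy-related count passes and the any-emesis count fails.

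**5. Part I power on the any-emesis definition, same boundaries.** With the formula in step 1: 0.809 at 5/19 and 0.894 at 29%, against 0.951 at 32%. These are design-stage figures. Given the responses already seen, step 4 is the relevant calculation.

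**6. Part II.** Exact Fisher power at the sizes in Table 1 (78, 39, 31 and 24 per arm) is 0.805, 0.802, 0.816 and 0.804, so the table reproduces. As an illustration, suppose Part I ended at 32%. Table 1 has no such column; the smallest size per arm is 66 (power 0.803 against 11%). If Part II is then scored on any emesis:

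| Arm B rate | Power, 66 per arm, Arm A at 5/19 | Power, 66 per arm, Arm A at 29% | Per arm for 80% power (5/19; 29%) |
|---|---|---|---|
| 11% | 0.547 | 0.681 | 110; 85 |
| 1/18 (assumed: the reference also loses one patient) | 0.894 | 0.946 | 54; 45 |

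The sign of the sizing error depends on how the 2/18 was scored. Section 11.0 does not say. Section 2.3, which cites the same references as the Part II sizing, reports rates for delayed nausea and vomiting without an emesis definition.

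**The case against.** The strongest reply is that Part I defines its own endpoint. The definition, the 6/19, the 32% target and the 8/42 rule stand together in one paragraph of Section 11.0, and a statistician applying the rule would use that paragraph. Section 9.3 is a general section covering several time windows, and the word that opens the Part II definition suggests shorthand for the Part I rule. The step to Part II is also worded as depending on Part I not being stopped early (with the supplier's consent, in Section 5.1), not plainly on 8/42. The observed gap is one patient in 19, and the exact 95% interval for 5/19 runs from 9.1% to 51.2%.

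Much of this stands. Part I is coherent on its own terms, and the Part II sizing harm is hypothetical: no section sizes Part II at 32%, and the 1/18 case is an assumption. The shorthand argument does not stand. Section 9.3 lacks the qualifier too, and Section 2.4.6 uses the unqualified wording as a separate measure with its own count: "the complete response rate (no emetic episodes and no rescue medications) was 29% (5/19".

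A reader might infer that Part II will be underpowered. The documents do not support that, because the direction is open. A reader might also infer that the Part I sample size is miscalculated, or that the misprinted 29% entered it. Neither is so: the design reproduces, and Section 11.0 uses 6/19.

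**Conclusion.** The point holds. The current text defines the primary endpoint in two ways, the two already give different counts, and no section says which governs throughout. Stage 1 is not affected.

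For the final Part I decision, the exposure is a chance of about 6% to 10% that the two definitions disagree on 8/42. This assumes that all 19 patients are evaluable, that 23 remain, and that future rates resemble the observed ones. With a gap of one patient it is an illustration, not an estimate.

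For Part II, what is established is a mismatch between the endpoint that would supply the sizing rate and the endpoint tested. Neither the size nor the sign of its effect can be fixed from the documents.

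The missing attribution rule is a defect in its own right for as long as the chemotherapy-related wording is kept. The 29% printed for 5/19 is a side correction in background text.

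**What to change.** Before the final Part I count, state one CR definition in Section 9.3 and in both parts of Section 11.0, and report the other as a sensitivity analysis.

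- **If the chemotherapy-related version is kept:** name the assessor, write the rule by which emesis is attributed to chemotherapy, and use it in both parts.
- **If any emesis is chosen:** the diary already supports it and no attribution is needed. Keep the 2/24 and 8/42 boundaries, record that the choice was made with both interim counts known, and restate Part I power (about 0.81 at 5/19 and 0.89 at 29%, against 0.95 at 32%).
- **In either case:** size Part II from Part I responses scored on the Part II definition, state how the 2/18 behind the 11% was scored, and correct either the fraction or the percentage in Section 2.4.6.

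The work is wording in two sections, a check of the 19 current and 18 reference patients against the chosen definition, and a recalculation. The real cost falls on the any-emesis option: it changes the Part I primary definition mid-trial, and the stated rate and power become less favourable. Keeping the chemotherapy-related version avoids that, but the primary endpoint then rests on an attribution judgement that in Part I is made knowing the treatment.

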5.0 Treatment Plan

5.1 Study Drug Treatment

This study will be conducted in 2 parts, part I and Part II, as follows:

Part I:

This part will be a single-arm phase II study of rolapitant administered as single-dose on Day 1. In this part, we will estimate the preliminary efficacy of rolapitant administered on day 1 by evaluating complete response (CR) in the single arm setting.

Up to 42 patients will be enrolled in part 1 (after the amendment 4) using the Simon's Minimax 2-stage design; 24 patients will be enrolled in the first stage. If \ge 2 out of 24 patients experience CR, additional 18 patients will be enrolled. The trial will be stopped early if less than 8 patients have complete response in nausea/vomiting.

With conclusion of Part 1 of study, communication of Part 1 study results will be presented to TerSera. In addition, publication of Part 1 study results may be presented for poster abstract and/or scientific journal for publication.

The decision to move on to Part II of this study will not depend on the results of the patients who have been treated with dexamethasone at 8 mg on Days 2-5. Rather, if the first part of the trial for the patients who will be treated with dexamethasone at 12 mg on Days 2-5 was not stopped early due to lack of efficacy of rolapitant and TerSera consents to continuation of the trial, the trial will proceed to the second part of the trial.

Treatment Plan:

All patients will receive anti-emetics approximately 1- 2 hrs prior to chemotherapy infusion as follow: Dexamethasone IV daily for 5 days (12 mg on days 1-5, after the amendment 2), Ondansetron (5HT3 receptor antagonist) 16 mg IV daily for 5 days as standard of care, and Rolapitant, 180 mg will be administered PO on Day 1. For 5-days Ifosfamide regimen, the anti-emetics will be given for 6 days.

Part II: This part will be a randomized, 2-arm phase II study of rolapitant vs fosaprepitant. If the trial was not stopped early, then the trial will proceed to the second part.

Assuming 40% and 11% CR rates in Arm A, and Arm B respectively, approximately 78 evaluable subjects will be randomly assigned to receive Rolapitant or fosaprepitant (1:1) administered as a single dose. The fosaprepitant arm will be used as standard arm to prevent patient selection bias.

Treatment Plan:

Patients will be randomized into two treatment arms: Arm A/ investigational arm: single dose of rolapitant n=39. Arm B/ control arm: single dose of fosaprepitant, n=39.

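### The 19 patients who set Part I's 32% target have already met its stage-1 boundary, so the printed 50% early stop, mean N of 33 and accrual halt no longer apply, and the remaining boundary is printed two ways

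*Combined protocol and SAP*

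**What the plan says.** Section 11.0, Part I, sets up a Simon minimax design. The null CR rate of 11% comes from 2 of 18 patients in a previous study. The target of 32% comes from this trial: "Based on the data of the 19 patients currently enrolled into this study, 6 out of 19 patients (32%) experienced CR". With both error rates at 0.05, the section gives a first stage of 24, rejection at 2 or fewer CRs, a further 18 patients otherwise, and a final rule: "the drug will be rejected if no more than 8 responses are observed in a total of 42 evaluable patients". It adds, for a true rate of 11%: "The trial will be stopped early 50% of the time, and the mean sample size of the trial will be 33". It also gives an operating instruction: "Accrual will be halted after the 24th patient is enrolled until 3 or more responses are seen in the first stage".

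The next paragraph of 11.0 assigns the same patients to stage 1: "19 patients have been enrolled and treated with dexamethasone at 12 mg on Days 2-5 as a new cohort for the first stage". Five more complete the 24, and "The same rules of the design aforementioned will be applied".

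Section 2.4.6 reports that all 28 patients enrolled so far (9 in the first dexamethasone cohort, 19 in the second) had finished more than one cycle. For the 19 it gives 6 CRs counting only chemotherapy-related emesis and 5 counting any emesis (printed as 29%, although 5/19 is 26.3%).

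Section 5.1 agrees that "24 patients will be enrolled in the first stage", but it lets the trial continue at 2 or more CRs, not 3, and then says: "The trial will be stopped early if less than 8 patients have complete response in nausea/vomiting".

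**The concern.** The endpoint is CR over days 1-10 of cycle 1. All 19 patients were past cycle 1, so 19 of the 24 stage-1 outcomes were known when the target and boundaries were written. Their CRs exceed either printed stage-1 boundary. The interim look that 11.0 describes is therefore spent, yet the section still presents its stopping probability, expected size and accrual halt as features of the trial ahead. A reader of 11.0 on the ethics board or at the drug supplier would think that an interim futility check is still to come.

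The rule at the end of Part I is then the only numerical efficacy check left in Part I, and sections 5.1 and 11.0 disagree on it by one response. Section 2.4.6 also says that the added patients are meant to confirm the response rate, and Part II is to be sized from the Part I rate. The 19 known outcomes that set the target make up 19/42 = 45% of that pooled rate.

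**Working it through.** **Inputs.** From 11.0: p0 = 0.11, p1 = 0.32, n1 = 24, stage-1 rejection at 2 or fewer, n = 42, final rejection at 8 or fewer. From 5.1: continue at 2 or more of 24; stop at fewer than 8. The 5.1 sentence names no denominator. It is read here as applying to all 42, because applied to the first 24 it would contradict 5.1's own continuation rule. From 2.4.6: 6/19 or 5/19.

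**Step 1: the plan's own figures, as a fresh design.** The early-stop probability at 11% is P(X ≤ 2), X ~ Bin(24, 0.11) = 0.0610 + 0.1810 + 0.2572 = 0.499. Mean N = 24 + (1 − 0.499) × 18 = 33.0. The chance of passing is the sum over x ≥ 3 of P(X = x) × P(Bin(18, p) ≥ 9 − x), which is 0.036 at 11% and 0.951 at 32%. An exhaustive search for the smallest n with type I error at most 0.05 and power at least 0.95 returns the same 2/24, 8/42 design. The printed figures reproduce.

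**Step 2: stage 1 as it stands.** At least 6 CRs (or 5) are already counted among the 24, whatever the last five patients show. Both counts exceed 2. Hence P(stage-1 stop) = 0, planned evaluable N = 42, and the condition for lifting the accrual halt is already satisfied.

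**Step 3: the two printed rule sets, each as a fresh design at 11%.**

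| Continue at | Pass at | Type I error |
|---|---|---|
| ≥3 of 24 | ≥9 of 42 (11.0) | 0.036 |
| ≥2 of 24 | ≥9 of 42 | 0.036 |
| ≥3 of 24 | ≥8 of 42 | 0.081 |
| ≥2 of 24 | ≥8 of 42 (5.1) | 0.084 |

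Almost all of the excess over 0.05 comes from the final boundary.

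**Step 4: conditional chance of meeting the final boundary.** New patients = 42 − 19 = 23. From 6/19, the 11.0 rule needs 9 − 6 = 3 more CRs and the 5.1 rule 8 − 6 = 2. From 5/19 they need 4 and 3. At 11%, for example, P(Bin(23, 0.11) ≥ 3) = 1 − (0.0685 + 0.1949 + 0.2649) = 0.472.

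| Start | Rule | More CRs needed | True 11% | True 20% | True 32% |
|---|---|---|---|---|---|
| 6/19 | 11.0 | 3 | 0.47 | 0.87 | 0.99 |
| 6/19 | 5.1 | 2 | 0.74 | 0.96 | 0.998 |
| 5/19 | 11.0 | 4 | 0.24 | 0.70 | 0.96 |
| 5/19 | 5.1 | 3 | 0.47 | 0.87 | 0.99 |

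**Step 5: what the 19 say on their own.** At a true 11%, P(6 or more of 19) = 0.0135, and the joint probability of that and at least 9 of 42 is 0.0073. The exact 95% interval for 6/19 is 12.6% to 56.6%; for 5/19 it is 9.1% to 51.2%.

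**The case against.** No printed figure is miscalculated. The 50% and 33 are given for a true rate of 11%, and they are correct. The 19 patients, their CRs and their place in stage 1 are all disclosed, so a reader can compare 6 with 2. Simon designs always pool the first stage into the final estimate, Part I aims only at a preliminary estimate, and the comparative test is in Part II. All of this stands. It makes the point one of correcting descriptions, not of invalidating the design. But the statements remain in 11.0 as current properties and as a live accrual instruction, and nowhere does the plan say that the boundary is met.

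Three stronger readings are tempting and are not supported.

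- **That type I error has risen to 0.47 or 0.74.** Those are chances from here on, given data already seen. The null comes from a previous study, and 6 or more of 19 would be unusual at 11% (0.0135).
- **That failing the final boundary certainly blocks Part II.** Section 11.0 sends the trial to Part II unless Part I was halted early for want of efficacy. It uses early stopping for the stage-1 event and rejection for the result at 42. Only the ambiguous sentence in 5.1 joins early stopping to a count near the final boundary, and 5.1 also requires the supplier's agreement. The Step 4 figures are chances of meeting a boundary, not of entering Part II.
- **That pooling will undersize Part II.** Table 1 starts at 30%. From 6/19, reaching a pooled 30% takes at least 7 CRs in the 23 new patients. At 7 the rates are 7/23 = 30.4% new and 13/42 = 31.0% pooled. At 8 they are 34.8% and 33.3%, and beyond that the pooled rate stays the lower. Within Table 1's range, pooling changes the rate little or lowers it.

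**Conclusion.** The concern holds as a fault in how the plan describes and fixes its Part I rules. On either CR count and either printed boundary, stage 1 is already passed: the stage-1 stop probability is 0, not 50%; planned evaluable N is 42, not a mean of 33; and the accrual halt has no effect. The boundary that remains differs between sections by one response. In a fresh design that moves type I error from 0.036 to 0.084, above the stated 0.05. From 6/19 at a true 11%, it moves the conditional chance of passing from 0.47 to 0.74 (from 5/19, 0.24 to 0.47).

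This rests on three assumptions: all 19 patients are evaluable, as the printed denominators imply; responses are independent with a common rate; and the 5.1 threshold of 8 applies to 42 patients. The Step 2 result does not depend on the third. It is not shown that the drug is inactive, that the error rate is inflated by reusing the 19, or that Part II will be too small.

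**What to change.** In sections 11.0 and 5.1:

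1. State that the 19 patients set the 32% target and that the stage-1 boundary is already met.
2. Delete the 50%, mean-33 and accrual-halt statements, or label them as properties of a fresh design, and give planned evaluable N as 42.
3. Reconcile 5.1 with 11.0 so that one stage-1 and one final boundary apply, consistent with the stated 0.05/0.05 calculation. Use the 6/19 count, which matches the Part I CR definition in 11.0, or reconcile it with 5/19. Say whether the final boundary gates Part II.
4. Report the CR rate with exact 95% interval for the 23 new patients beside the pooled 42, and say which of the two feeds the Part II sample size.

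The cost is text changes and one extra estimate. No Part I patients are added. Item 3 does withdraw one of two conflicting printed rules, so it needs a decision by the sponsor and not just an edit. It is best made before the remaining 23 outcomes are known.
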